3. Advances in asynchronous online simulation training points us towards novel solutions to developing and testing a streamlined, user-friendly, approach to training long-term care providers on the implementation of an evidence-based program that is not dependent upon labor-intensive face-to-face training and intensive involvement of the developers of the original program. Thus, this study will have great impact in guiding future efforts to scale evidence into practice by providing a model for scalable approaches to training providers in evidence-based approaches.
4. We will capitalize on recent technological advances by developing an automated process for fidelity monitoring based in natural language processing methods, and advances in statistical text analysis and behavioral science expertise to produce a computational tool to support and extend the capacity for large-scale fidelity monitoring. Historically, the research gold standard for evaluating fidelity has been human coding applying a theory driven rubric to identify relevant activities. This type of coding requires the training of human readers, establishing inter-rater reliability, and then performing the time-consuming task of coding. This reliance on human judgment for fidelity has been labor intensive, expensive, and has impeded the ability to study widespread dissemination efforts. As a result, it has been impossible to evaluate fidelity in large-scale pragmatic trials in any systematic ongoing manner. The proposed study examines a novel methodology for automating evaluation of clinician fidelity to an evidence-based program that could be used by clinical settings as a systematic approach for quality assurance.

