serve as the control site in which training will be provided via the virtual/remote training lead by a trained OT; 5 PACE organizations will serve as the comparison and be trained through the online training site. Prior to randomization, we will carefully examine PACE organizations on important variables such as size, location (urban; rural) percent of persons with dementia, and staff: participant ratio. In each site, one occupational therapist (OT) and one nurse (RN) will be trained (e.g., 5 OTs and 5 RNs in virtual/remote training sites; 5 OTs and 5 RNs in online training sites for a total of 10 OTs and 10 RNs or 20 health providers) Re-randomization procedures. Because COPE will be delivered by PACE staff to multiple participants with dementia within each organization, randomization at the individual participant level could lead to significant contamination between treatment and control conditions within an organization. Prior to randomization, we will collect organization-level data and have measures of organization size (or capacity), location (urban, suburban, rural), and summary characteristics of the participant population at each organization (e.g., percentage with dementia diagnosis, percentage minority). Because we will randomize ten organizations to five virtual/remote and five online training organizations, notable and problematic imbalances on at least a few organization-level characteristics could easily occur by chance in a single randomization. Methodological innovations are needed to achieve balance on these multiple organization-level characteristics while still maintaining the experimental rigor and inferential value of true random assignment. [name] will implement a re-randomization approach to achieve these important methodological goals. The balance match weighted (BMW) design is an innovative re-randomization procedure that is particularly well suited to our goals (54). Using the BMW approach, we will: 1) finalize the list of important covariates for which we desire matching or balancing across intervention and control organizations, 2) generate 20 lists of random assignments for these 10 organizations into intervention and control conditions, 3) calculate propensity scores of intervention assignment as a function of the covariates, and 4) select the random assignment list that minimizes the propensity score differences between intervention and control organizations. The BMW approach provides a random assignment distribution that has an optimal balance on multiple organization-level characteristics. This will result in even greater control over potential covariate influences and provide somewhat greater power to detect a COPE program effect. Treatment Conditions: COPE Online Training: Trinity PACE Organizations assigned to the COPE Online Training will receive the 10- Module training program described above. Designated OT/ RNs at the assigned PACE Organization will be emailed unique log-in details and instructions for completing the online training within the 3-day training window (to align with control group training) but at their own pace. Log-in details including date, time and duration in training sessions will be tracked. COPE Virtual/Remote Training: We will train one OT and one RN at each of the five PACE organizations randomly assigned to the virtual/remote training. [name] will conduct trainings. Our training program will involve up to 3 days which include about 4 hours of initial readings, PowerPoint presentations, and case presentations. Training will take place via web conference (via GoToMeeting.com or other platform) sessions. We will offer three of these training sessions to accommodate COPE staff members' schedules and assure an interactive process. Further, interventionists will participate initially in monthly tele-conference or web conference sessions and then 6 times a year over the duration of intervention delivery. Sessions will involve case presentations, troubleshooting, and adherence monitoring. We have used this approach in multi-organization endeavors with up to 15 interventionists actively participating by telephone. Using a structured agenda and assigning case presentations a priori facilitates productive discussions. We have allocated funds for COPE staff members time to participate in training and follow-up bimonthly calls to troubleshoot cases. Both groups will participate in monthly debriefing sessions which will be recorded and used to understand type of questions asked, problems encountered etc., to compare the two training groups. We have a specific agenda and methodology for interventionists to provide case reports (55). We will also establish a password secure and encrypted email list serve for interventionists to post challenges and receive feedback from PIs and other interventionists.

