to be provided to the DSMC for this proposed trial. Primary responsibilities: The DSMC will be responsible for reviewing the safety of study participants during the conduct of this study and provide recommendations to the research team on specific aspects of the research protocol as it pertains to safety, potential study alerts and adverse events. Specific responsibilities of the DSMC will be to: a) provide an independent periodic review of recruitment and enrollment progress; b) review adverse events (AEs) including serious events and offer recommendations regarding the trial based on such observed events; c) serve in a consultative capacity to the research team regarding study procedures to address ethical dilemmas (e.g., reporting of abuse), safety of subjects in the trial, and appropriateness of all study procedures. Composition of the DSMC: The DSMC will be an independent multi-disciplinary group consisting of biostatistical, applied research and clinical experts who collectively have experience in practical trial designs, multi-site trials and mixed methods. The 3 to 5 member board will have no apparent conflict of interest with the investigative team or study including financial, scientific or regulatory in nature. DSMC members will be responsible for advising the PIs of any changes in their relationship and/or financial interests that occur during the course of the trial. The DSMC and PIs will be responsible for deciding whether these changes create a conflict of interest. Any DSMC member who develops a conflict of interest during the course of the trial will be asked to resign from the DSMC and another person with similar areas of expertise will be sought. Otherwise, DSMC membership is to be for the duration of the trial. DSMC Meetings, Documentation: We propose that the DSMC have one face-to-face meeting prior to entering into the field for the trial and one teleconference call each subsequent year unless the DSMC decides and votes otherwise at its first organizational meeting. More frequent meetings or teleconferences may be held in the rare need to review serious adverse events from the trial at the discretion of the DSMC. At the initial meeting in year 01 (anticipated to occur in month 5 prior to entry into the field), the DSMC will review all study procedures including data collection forms, intervention protocol and oversight plan. At this meeting, the DSMC will agree on whether there should be interim analyses, and if so, the stopping rules and interim analysis plan that avoids potentially biasing the investigative team. Modifications to protocols based on the DSMC review will be made prior to entering the field. At subsequent conference calls, the DSMC will review the progress of the study (accrual rate, protocol deviations and interim study analyses if recommended) and make recommendations. A representative of the research team will keep minutes of these meetings. A copy of the minutes approved by the DSMC will be shared with the IRB of UPENN. The minutes will include recommendations of the DSMC and be provided to the NIH after each meeting. Meetings of the DSMC will be open unless the DSMC requests otherwise. A closed meeting of the DSMC may be requested if it is deemed necessary to review outcomes data. The DSMC chair or their designate will take meeting notes of closed sessions. Provision of Data for DSMC Review. Interim Analyses: We elect not to consider interim analyses in this study due to the extended time for recruitment and the low likelihood of a sufficiently large effect that would make it possible to stop early. This study is designed as a non-inferiority trial in which two different training methodologies are being evaluated. Outcomes of the COPE program for people with dementia and caregivers are secondary and serve to confirm (or not) whether the online training approach is as good or better than traditional face-to-face intensive training. However, we will revisit this decision with the DSMC at its first organizational meeting. Adverse Event (AE) Reporting: The DSMC will be notified by the PI of any serious AE within 48 hours of initial notification to the project team that is attributed to the intervention (low or high probability). All members of the DSMC will receive copies of all safety reports at the time of their submission to the IRB. Safety Monitoring Plan: We do not anticipate any adverse reactions to the training approaches or implementation of the COPE program. Based on our previous work and studies in this area by others, there is only a small risk that family caregivers or persons with dementia will become increasingly anxious to the point that it becomes an adverse event (e.g., harmful to self or others) as a consequence of the COPE program. However, interviewers/ interventionists will be well trained to manage this reaction or make an effective referral if necessary and documentation of all such events will occur. Recruitment and AE Reports: Reports presented to the DSMC will include data on enrollment (study accrual by month; comparison of expected to actual enrollment; number of individuals screened, number eligible and number ineligible, number randomized by gender, and AEs. Also, the DSMC will receive reports of the number of study participants who discontinue from each study arm (those receiving COPE from interventionists trained via face-to-face/virtual versus those receiving COPE from interventionists trained via online program) and/or the study and reasons for discontinuation. We propose that reports be provided to the DSMC twice yearly. However, the DSMC will decide upon the schedule of

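### A single list serve for interventionists, not split by training arm, permits peer coaching across arms during delivery and can bias Aims 2 and 3 towards non-inferiority

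*Combined protocol and SAP*

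**What the plan says.** The same arrangement appears twice: in the Research Plan (Phase 2, Treatment Conditions) and in Study Procedures (Phase 2).

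- **List serve.** The team will set up a secure "email list serve for interventionists to post challenges and receive feedback from PIs and other interventionists". No membership rule by arm is given.
- **Debriefings.** The sentence that opens the same paragraph reads "Both groups will participate in monthly debriefing sessions which will be recorded and used to understand type of questions asked", and adds that the recordings serve to compare the two training groups. Whether sessions are joint or by arm is not said.
- **Follow-up calls.** Under the virtual/remote condition, "interventionists will participate initially in monthly tele-conference or web conference sessions and then 6 times a year over the duration of intervention delivery". The description of the online condition mentions no such calls.
- **Contamination.** Organizations are the unit of randomization because "randomization at the individual participant level could lead to significant contamination between treatment and control conditions within an organization". Contact between organizations in different arms is not addressed there or in the Analysis Plan.
- **Objective.** Under Data and Safety Monitoring: "This study is designed as a non-inferiority trial in which two different training methodologies are being evaluated". The Innovation list describes the online approach as "not dependent upon labor-intensive face-to-face training and intensive involvement of the developers of the original program".

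**The concern.** The plan gives up individual randomization to keep the two training conditions apart inside an organization. It then opens a channel between organizations whose stated purpose includes feedback from peers. With 20 trained staff in all, 10 per arm, a few active contributors could reach everyone.

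The timing matters. Fidelity is rated on sessions recorded during delivery, and dyad outcomes are assessed at 4 months; both arise while the list is meant to be in use. If online training were worse, advice from peers trained by the other method could make up part of the shortfall. In a superiority trial that would cost power. Here it makes a wrong claim of non-inferiority more likely.

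Investigator feedback raises a second question. Given equally to both arms, it is a co-intervention and not contamination, but it changes what is compared: training followed by expert support, rather than training alone. That sits uneasily with a program promoted as needing little involvement from its developers.

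**Working it through.** **Plan's own figure.** There is none to reproduce. The available text gives no margin, SD, alpha, power or allowance for dilution. The counts do agree: 10 organizations × 5 dyads = 50 (25 per arm), and 10 × 2 staff = 20 (10 per arm).

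**Inputs**

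- From the documents: 25 dyads per arm (Phase 3); 10 staff per arm (Phase 2); one-sided two-sample t-tests for non-inferiority at 4 months (Analysis of Aim 3).
- Assumed: margin M of 0.3, 0.5 or 0.8 SD; one-sided alpha 0.05 (0.025 as an alternative); a true deficit from training alone exactly equal to M; a share c of it erased by cross-arm contact; independent observations.

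**Formula (normal approximation, SD units).** SE = √(2/n). After sharing, the true difference is M(1 − c), so its distance from the margin is cM, and

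P(declare non-inferiority) = Φ(cM/SE − z₁₋α).

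At c = 0 this equals alpha. For any c > 0 and any M > 0 it exceeds alpha. The direction therefore does not depend on the assumed margin or alpha.

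**Worked case.** n = 25: SE = √(2/25) = 0.283. With M = 0.5, c = 0.5 and alpha 0.05: 0.25/0.283 = 0.884; 0.884 − 1.645 = −0.761; Φ = 22.3%.

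**Results, 25 dyads per arm, one-sided alpha 0.05**

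| Margin (SD) | c = 0 | c = 0.25 | c = 0.50 | c = 0.75 |
|---|---|---|---|---|
| 0.3 | 5.0% | 8.4% | 13.3% | 19.8% |
| 0.5 | 5.0% | 11.5% | 22.3% | 37.5% |
| 0.8 | 5.0% | 17.4% | 40.9% | 68.3% |

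**Sensitivity at c = 0.5**

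- Alpha 0.025, 25 per arm: 7.6%, 14.1% and 29.3% for margins of 0.3, 0.5 and 0.8 SD, against 2.5% without sharing.
- Non-central t in place of the normal approximation, alpha 0.05, 25 per arm: 13%, 22% and 40%.
- Assumed intracluster correlation 0.05 with 5 dyads per organization, design effect 1 + 4 × 0.05 = 1.2, allowed for in the SE, alpha 0.05: 12.3%, 20.1% and 36.2%.
- 10 staff per arm, margin 0.5 SD: 13.9% (alpha 0.05) or 8.1% (alpha 0.025).

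None of these models the Aim 2 comparison of recorded sessions, for which the plan names no between-arm test.

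**The case against.** **The text does not say that the arms share one list.** True: separate lists are not expressly ruled out, and no level of use is specified. A reader might infer that the plan prescribes cross-arm coaching; it does not. It does describe one list for interventionists without restriction, straight after a sentence about both groups, with peer feedback as a purpose. One shared list is the natural reading, and a team following the text would have no reason to build two.

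**Debriefings.** A reader might infer that these are joint. The documents do not support that: recordings used to compare the groups fit sessions held by arm at least as well. The point rests on the list serve; the debriefings need only a clarifying statement.

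**Aim 1.** It is tempting to extend the bias to every aim. Knowledge, competency and satisfaction are measured around training, so a channel for problems met in delivery should affect them little if the post survey comes directly afterwards. Its timing is not stated. Dyad outcomes are called secondary in the monitoring section, so the main exposure is Aim 2.

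**The percentages are not from this trial.** Correct. Margin, alpha and dilution are all assumed. The model also takes the net effect of contact to be a narrowing of a deficit; contact that mainly helped the control arm would not do that.

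**Separate lists leave investigator feedback in place.** Also correct. That part is a matter of defining the comparison, not of separating the arms.

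**Follow-up contact.** A reader might see contradictory schedules. Six times a year and bimonthly can mean the same thing, and the monthly debriefings for both groups may be a separate activity. What remains open is whether the calls described under the virtual/remote arm also apply to the online arm.

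**Conclusion.** The concern holds for the list serve. As written, it allows peer coaching across arms during delivery, no safeguard or analysis addresses this, and any net narrowing of a true online deficit raises the chance of a false non-inferiority finding in Aims 2 and 3. That direction needs no assumption about margin or alpha. The size cannot be determined from the documents. The rise from 5% to about 13–41% is an illustration that depends on half of the deficit being erased, 25 independent dyads per arm, one-sided alpha 0.05 and margins of 0.3–0.8 SD; it should not be read as this trial's error rate. The documents do not establish that debriefings are joint, that Aim 1 is materially affected, or that cross-arm coaching took place.

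**What to change.** **If delivery is still to come or under way**

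- Run one list serve per training arm.
- State that debriefings are held by arm, with the same agenda and number of sessions.
- Ask staff not to share training content across arms.
- Log posts, investigator feedback and attendance by arm.
- State that the comparison is of training plus the ongoing investigator support given to both arms.
- Say whether the follow-up calls listed under the virtual/remote condition also apply to the online condition.

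**If delivery has already occurred.** This is possible: the Consent Process refers to staff who signed before September 2022, and the protocol is dated January 2025. In that case, classify existing posts and attendance by arm, report fidelity from early sessions as a sensitivity analysis, and state cross-arm contact as a limitation.

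**Cost.** A second mailing list, separately scheduled calls and some logging. No extra participants are needed. The early-session analysis uses fewer recordings and will be less precise.

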
**PHASE 3 (Aim 3): Efficacy of COPE on PACE participant outcomes by type of COPE training.**  
This aim will be accomplished by evaluating dyad outcomes of the COPE program under the two different training approaches. Following training, each of the PACE organizations will enroll 5 persons with dementia and their caregivers in the study. This will yield 50 family dyads (25 dyads in traditional training sites and 25 dyads in online training sites). At 4 months, all dyad study outcomes will be assessed

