**Most participants in Programs of All- Inclusive Care of the Elderly (PACE) have dementia, yet to date, evidence-based programs have not been integrated into their service mix (23,24).** PACE provides comprehensive long-term care services and supports to nursing home eligible Medicaid and Medicare enrollees in the community so that elders can remain in their homes (24). Dementia is an independent risk factor for nursing home admission in numerous studies of community-dwelling older adults, even when controlling for numerous comorbidities (25). Among PACE participants with dementia, functional disability and family caregiver physical and emotional strain, are the most important predictors of nursing home admission pointing to the need to keep older adults with dementia at the highest levels of functioning as possible to remain living at home (26). Physical and emotional burdens of providing help with activities of daily living, as well as the challenges of managing disruptive behaviors such as wandering and resistance to care, place CGs at risk for depression, physical health problems, and admitting their relative to a nursing home (25). Thus, PACE is an important test bed for integrating evidence-based programs that can delay or avoid nursing home admissions. Nonetheless, the gap between the dementia care evidence-base and community-based dementia care has long been noted in the literature (26). Despite tremendous strides in developing and testing community-based programs for persons with dementia, they have been tested outside of existing service and funding streams. Also, there has been little study of strategies for effective dissemination of evidence-based interventions and impact on adoption by community-based long-term care settings such as PACE (27,28).

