5. Partnering with Trinity PACE, the largest PACE provider in the US, will provide robust, generalizable data. The development of this proposal reflects extensive collaboration among study team members and Trinity Health. Trinity Health PACE is a member of Trinity Health, one of the largest multi-institutional Catholic health care delivery systems in the US. Trinity Health PACE is one of the leading providers of PACE in the country based on the number of available programs. In preparation for this application, during meetings with Trinity Health and Trinity PACE leadership, leaders, administrators and staff all demonstrated clear engagement, and expressed keen interest in improving dementia care practices, and a readiness and capacity for change. In preparation for this RFA 10 Trinity Health PACE organizations expressed willingness to participate (see Letter of Support). PACE Organizations for participation in this trial fit these criteria: a) have a minimum of 90 enrolled participants; b) have OT and RN staff; and c) express willingness to participate and accept random assignment. The lessons learned in this study concerning training and fidelity methodologies will enable us to move rapidly forward with a large, multi-site pragmatic trial to test embedding COPE within existing Trinity PACE. As Trinity PACE Organizations will be highly generalizable to all PACE programs nationally as they all have similar financial and clinical

structures regardless of their management organization nationally.

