**Consent Process:** All informed consent guidelines of the University of Pennsylvania Institutional Review Board (IRB) will be followed. We will use a multi-stepped approach to gaining consent from Trinity Health PACE occupational therapists and nurses (OT/RNs) using email, DocuSign, PennBox, or mail to obtain consent signatures. The Penn site will obtain consent from OT/RNs who agree to complete the training program. Discussions about consent will take place between the study team and OT/RN participants via phone and video conferencing programs (Skype, FaceTime, Blue Jeans, Zoom, etc.). Two Trinity Health PACE sites will participate in a pilot test of all study procedures. OTs and RNs from these sites will sign the "OT and RN ICF Pilot Test" document. This version of the ICF notes that these participants will participate in the pilot test or beta test. Then, recruitment of caregivers will be done by Trinity research liaisons who will read a Penn-approved recruitment script to caregivers or share flyers with study team contact information to use. Interested caregivers will contact study team members (if received flyer) or be contacted via telephone by Penn study team members (if consented to have their contact shared) who will provide more detail about the study, answer questions, and read the caregiver verbal consent script. Within the script is language that informs the caregiver that 1) the

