OT and research team will record and transcribe COPE sessions and interviews with dyads for quality and assurance purposes, and 2) the research team will collect patient data from the Trinity Health PACE medical record for research purposes. The objectives, procedures, and a clear statement explaining risks and benefits of this study will be presented via the consent script. Caregivers who consent verbally will be emailed or mailed a copy of the consent script which has been signed by the Penn researcher obtaining consent. If caregivers consent to participant, caregivers will be screened for eligibility. Caregivers will be informed that the screen is confidential and completely voluntary. All call notes, consent forms and telephone screens will be performed and housed in REDCap or on a Penn-approved secure server. Penn will house all recruitment and consent forms and assume responsibility for any and all modification of ICFs. For those initially eligible based on the telephone screen and who consent to participate, a full baseline telephone interview will be conducted either following the screen or at a time more convenient for the caregiver but within one week of completing the screen.

Regardless of when the baseline interview is conducted, the interviewer will again obtain verbal consent from the family caregiver for their participation. Participants who currently active or in the follow-up stage will need to re-consent to participate. Caregivers who originally consented prior to September 18th, 2022, will be called and read the additional information added to the consent form and asked if they have any questions. Once all questions have been answered, caregivers will be asked to verbally consent. Once confirmation of consent is received over the phone, caregivers will receive an updated copy of the written statement of research. Staff participants (occupational therapists and registered nurses) who have signed consent forms prior to September 16th, 2022 will need to be re-consented. These participants will receive an email with the new consent language listed and a blank copy of the updated consent form attached. Staff participants will be asked to follow up with any questions they have. If participants do not have questions or all questions have been answered, participants will be asked to sign the form and send back to Penn researchers.

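### Dyads are recruited after sites are randomized and trained, with no approach order or masking of recruiters, and the unadjusted Aim 3 test cannot absorb a resulting difference in case mix

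*Combined protocol and SAP*

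**What the plan says.** **Order of events.** Under Study Procedures, Phase 2, "we will randomize ten organizations to five virtual/remote and five online training organizations", and one OT and one RN per organization are trained. Phase 3 then states: "Following training, each of the PACE organizations will enroll 5 persons with dementia and their caregivers in the study".

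**Who makes contact.** The Consent Process section says that "recruitment of caregivers will be done by Trinity research liaisons who will read a Penn-approved recruitment script to caregivers or share flyers". Caregivers given a flyer contact the study team themselves. Others are telephoned by the study team if they agreed to have their contact details passed on. The study team takes verbal consent, and the eligibility screen follows: "If caregivers consent to participant, caregivers will be screened for eligibility".

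**Pool.** Item 5 of the Innovation list requires that organizations "have a minimum of 90 enrolled participants". The Significance section says: "Most participants in Programs of All- Inclusive Care of the Elderly (PACE) have dementia". No number of eligible dyads is given.

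**Balance and analysis.** The re-randomization procedure uses organization size, location and summary features of each site's population. The Analysis Plan tests Aim 3 by one-sided two-sample t-tests at 4 months, with no baseline or site term. Study Instruments lists the dyad measures as collected at both baseline and four months.

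**The concern.** In a cluster-randomized trial, randomization protects the comparison of sites. It does not protect the comparison of people who are identified and invited after the site's allocation is in effect. Here all dyads enter that way. If the families put forward differ between arms in severity, caregiver capacity or willingness, the arms differ before the first COPE session, and balancing organization-level covariates cannot correct this.

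All families receive COPE and the arms differ only in how staff were trained, so a modest difference in case mix could imitate or hide the contrast under study. In a non-inferiority comparison, easier dyads in the online arm push toward a false claim of non-inferiority. Harder dyads there push toward missing a true one. Aim 2 compares fidelity in sessions held with the same dyads, so it could be affected as well.

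**Working it through.** **1. The plan's own figures.** 10 organizations x 5 = 50 dyads, and 5 x 5 = 25 per arm, as stated. The 600 recorded sessions of Aim 2 equal 50 x (10 OT sessions + 2 RN visits), so they fit sessions held with these same dyads.

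**2. Does any provision control who is approached?**
- Study-team screen: it follows approach and consent, so it filters only those who already came forward.
- Re-randomization: organization-level covariates only, fixed before any dyad is known.
- Data and Safety Monitoring reports: they count persons screened, eligible and ineligible, not those never approached.
- Blinding sentence in the same section: it concerns the PI and investigative team when the DSMC asks for unblinded data. Liaisons and site staff are not mentioned.
- Analysis Plan: arms are compared descriptively at each timepoint, but no adjustment follows.

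**3. How much room is there for selection?** At a minimum-size site, if half have dementia, 90 x 0.5 = 45 persons, and 5/45 = 11%. That counts persons with dementia, not eligible dyads. If half of them form an eligible dyad the pool is 22.5 and the fraction 22%. If a quarter do, it is 11.25 and 44%.

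As an extreme bound, suppose every site in one arm enrolled its five most favourable dyads and the other arm's dyads were typical. The mean of the top five of a normal sample (simulation, 100,000 draws), times an assumed correlation of 0.2 with the outcome, gives:

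| Pool | Mean of top five (SD) | Shift in outcome (SD) |
|---|---|---|
| 45 | 1.66 | 0.33 |
| 23 | 1.30 | 0.26 |
| 11 | 0.81 | 0.16 |

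So a material shift is possible even with a small pool.

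**4. What would a given bias do?** The plan states no alpha, margin, SD or power for Aim 3, so the following values are assumed: one-sided 5%, 25 independent dyads per arm, and bias = baseline shift x correlation of baseline with outcome. The standard error is sqrt(2/25) = 0.283 SD. At the margin, the rejection rate is P(T > 1.677), where T is non-central t with 48 df and non-centrality bias/0.283. The margin itself cancels.

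| Baseline shift (SD) | Correlation | Bias (SD) | Rate at one-sided 5% | Rate at one-sided 2.5% |
|---|---|---|---|---|
| 0 | - | 0 | 5.0% | 2.5% |
| 0.2 | 0.5 | 0.10 | 9.7% | 5.3% |
| 0.2 | 0.7 | 0.14 | 12.4% | 7.0% |
| 0.3 | 0.5 | 0.15 | 13.1% | 7.5% |
| 0.3 | 0.7 | 0.21 | 18.1% | 10.9% |

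With the sign reversed, the same formula at one-sided 5% gives 2.3% for a bias of -0.10 SD and 0.9% for -0.21 SD, so the test is conservative. With an assumed intracluster correlation of 0.05 allowed for in the test, the standard error is 0.283 x sqrt(1 + 4 x 0.05) = 0.310 SD. A 0.10 SD bias then gives 9.3% (normal approximation).

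**The case against.** The strongest reply is that no one is shown to select. The liaisons are described as Trinity liaisons, not as the trained OTs or RNs, and nothing says they know the arm. Flyers let caregivers refer themselves, and the study team takes consent and screens. Interventionists in both arms must be certified as competent, both arms have debriefing sessions, and every family receives COPE, so the usual motive for differential recruitment is weak. Dyad outcomes are described as secondary, and Aim 1 does not depend on dyads.

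Much of this stands. A reader might infer that site liaisons who know the arm pick five out of 45 or more possible dyads. The documents do not support that. Knowledge of the arm is not stated, liaisons inform rather than choose, and 45 is a count of persons with dementia under an assumed 50% share, so eligible dyads may be fewer. Nor do the documents support a bias in favour of the online arm in particular. The kappa agreement between automated and human ratings is not an arm comparison and is less exposed.

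What the reply does not remove is the open route. Training takes place before recruitment at each organization, and nothing in the text keeps knowledge of the arm from influencing who is told of the study or how warmly. Self-referral after allocation is not protected by randomization either.

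A practical objection also stands. The document is dated January 2025 and describes re-consenting people enrolled before September 2022, so a list made before allocation may no longer be possible.

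**Conclusion.** The concern holds as a risk left uncontrolled, not as a demonstrated bias. Recruitment follows randomization and training, no approach order or masking of recruiters is set, balancing stops at organization level, and the Aim 3 test makes no use of the baselines collected. A difference in the dyads put forward would bias Aim 3 and could reach the Aim 2 arm comparison of fidelity, an effect not quantified here.

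The size is illustrative: about 10-18% instead of 5% at the margin for a bias of 0.10 to 0.21 SD toward the online arm. It rests on the assumed shifts, correlations, alpha and independence of dyads. The direction is unknown.

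The statements about what is absent are limited to the text available, which lacks part of the Approach section and Table 2. Because dyad outcomes are secondary, this should be corrected but does not undermine the trial as a whole.

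**What to change.** - **Before allocation is disclosed:** each organization lists its participants with dementia and a family caregiver under codes held at the site. The study team sees only the codes and puts them in random order. Liaisons invite in that order until five dyads enrol, unaware of the arm where practical. Site-held codes respect the rule that contact details are shared only with the caregiver's agreement.
- **Reporting:** give numbers listed, approached, eligible, refused and enrolled, by arm, and state whether recruiters knew the arm.
- **Analysis:** adjust each Aim 3 comparison for the baseline value of that outcome. This removes only the part of a case-mix difference that the baseline measures capture.
- **If recruitment is already complete:** the recruitment flow, as far as records allow, and the baseline adjustment still apply.

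The number of dyads stays at 50. The cost is one list per organization (the plan now gathers only summary characteristics before randomization), a contact log, some liaison effort, and topping up the list when participants leave before invitation. Baseline adjustment needs no new data.
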